4.1 General considerations

4.1.1 Baseline definition

Unless stated otherwise, baseline is defined as the pre-dose assessment taken at Visit 2. For FACIT, HAQ-DI and Tender/swollen joints assessments baseline is defined on the questionnaire level, not on an individual measurements level.

For quantitative measurements, change and percent change from baseline will be calculated as:

- Change from baseline = Post-baseline value – Baseline value
- Percent change from baseline = $100\% * (\text{Post-baseline value} - \text{Baseline value}) / \text{Baseline value}$ for baseline values greater than 0.

Changes from baseline will only be summarized for patients having both baseline and post baseline values.

For the changes from Week 24 at Week 48 in terms of DAS28-CRP, DAS28-ESR, HAQ-DI score, and FACIT Fatigue scale, the nominal Week 24 and Week 48 visit values will be used.

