## Glossary of terms

Assessment	A procedure used to generate data required by the study.
Baseline	Assessments taken during Visit 2/Randomization
Control drug	A study drug used as a comparator to reduce assessment bias, preserve blinding of investigational drug, assess internal study validity, and/or evaluate comparative effects of the investigational drug.
Enrollment	Point/time of patient entry into the study; the point at which informed consent (ICF) must be obtained (i.e. prior to starting any of the procedures described in the protocol)
Investigational drug	The study drug whose properties are being tested in the study; this definition is consistent with US 21CFR 312.3 and is synonymous with "investigational new drug."
Medication number	A unique identifier on the label of each medication package in studies that dispense medication using an Interactive Response Technology (IRT) system.
Patient number	A number assigned to each patient who enrolls in the study. When combined with the center number, a unique identifier is created for each patient in the study.
Period	A minor subdivision of the study timeline; divides phases into smaller functional segments such as screening, baseline, treatment, titration, washout, etc.
Premature patient withdrawal	Point/time when the patient exits from the study prior to the planned completion of all study drug administration and/or assessments; at this time all study drug administration is discontinued and no further assessments are planned.
Randomization number	A unique identifier assigned to each randomized patient, corresponding to a specific treatment arm assignment.
Stage	A major subdivision of the study timeline; begins and ends with major study milestones such as enrollment, randomization, completion of treatment, etc.
Stop study participation	Point/time at which the patient came in for a final evaluation visit or when study drug was discontinued whichever is later.
Study drug	Any drug administered to the patient as part of the required study procedures; includes investigational drug and any control drugs.
Study drug discontinuation	Point/time when patient permanently stops taking study drug for any reason; may or may not also be the point/time of premature patient withdrawal.
Variable	Information used in the data analysis; derived directly or indirectly from data collected using specified assessments at specified time points.

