### **Study period 2: Week 24 - Week 48**

- To evaluate clinical safety in patients treated continuously with GP2017 and in patients treated with GP2017 after switch from US-licensed Humira® as assessed by changes in vital signs, clinical laboratory parameters and incidence and severity of AE
- To evaluate incidence and severity of injection site reactions (ISRs) in patients treated continuously with GP2017 and in patients treated with GP2017 after switch from US-licensed Humira®
- To evaluate immunogenicity as determined by measuring the incidence of ADA formation against adalimumab in patients treated continuously with GP2017 and in patients treated with GP2017 after switch from US-licensed Humira®
- To evaluate efficacy in patients treated continuously with GP2017 and in patients treated with GP2017 after switch from US-licensed Humira® as assessed by DAS28-CRP, DAS28-ESR score changes from Week 24 at Week 48 and ACR20/50/70 responses at Week 48
- To compare Health Assessment Questionnaire-Disability Index (HAQ-DI) changes from Week 24 at Week 48 in patients treated continuously with GP2017 and in patients treated with GP2017 after switch from US-licensed Humira®
- To compare the proportion of patients treated continuously with GP2017 and patients treated with GP2017 after switch from US-licensed Humira® achieving HAQ-DI score  $\leq 0.5$  at Week 48
- To compare Functional Assessment of Chronic Illness Therapy (FACIT) Fatigue scale changes from Week 24 at Week 48 in patients treated continuously with GP2017 and in patients treated with GP2017 after switch from US-licensed Humira®

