**Table 12-1 Notable laboratory values for subjects with value within limits of normal at baseline**

Laboratory variable	Standard units	SI units
Aspartate aminotransferase	> 3 x ULN	> 3 x ULN
Alanine aminotransferase	> 3 x ULN	> 3 x ULN
Total Bilirubin	> 1.5 x ULN	> 1.5 x ULN
Alkaline Phosphatase	> 2.5 x ULN	> 2.5 x ULN
Creatinine (serum)	> 50% above baseline	> 50% above baseline
Potassium	< 3.0 mEq/L > 6.0 mEq/L	< 3.0 mmol/L > 6.0 mmol/L
Sodium	< 130 mEq/L > 150 mEq/L	< 130 mmol/L > 150 mmol/L
Calcium	<8 mg/dL >11.5 mg/dL	<2 mmol/L >2.9 mmol/L
Hemoglobin	> 20 g/L decrease from baseline	> 20 g/L decrease from baseline
Red Blood Cell count	> 20% below baseline	> 20% below baseline
Platelet count	< LLN	< LLN
White Blood Cell count	< 0.8 x LLN	< 0.8 x LLN
Absolute Neutrophil count	< 0.9 x LLN	< 0.9 x LLN
Absolute Lymphocyte count	> 1.1 x ULN	> 1.1 x ULN
Total Cholesterol	≥ 350 mg/dL	≥ 9.1 mmol/L

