4.6.2.2 Laboratory data

Results from the central laboratory will be included in the reporting of this study. The summaries presenting a number of patients with new notable abnormalities (according to the protocol), as well as shift tables by toxicity grades will be presented for hematology and serum chemistry by treatment group for each Study Period. Standard units will be used for presentation. Box plots of parameters of interest will be done by treatment and study period. The laboratory results below the LLOQ will be imputed as zero, the laboratory results above the upper detection limit will be imputed as upper detection limit.

All laboratory data (including urinalysis) will be listed. Notable abnormalities will be listed in addition.

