4.6.2.3 Vital Signs

Vital signs measurement includes blood pressure (systolic and diastolic), pulse and temperature. The summary presenting a number of patients with new notable abnormalities (according to normal range criteria) will be presented by treatment group for each study period. All information collected will be listed. Notable abnormalities will be listed in addition.

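### Laboratory shift tables and baseline-relative limits for Study Period 2 are measured from Visit 2, before any treatment, not from before the switch

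*SAP*

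**What the plan says.** - **Baseline.** SAP 4.1.1: "Unless stated otherwise, baseline is defined as the pre-dose assessment taken at Visit 2". The protocol glossary agrees: "Assessments taken during Visit 2/Randomization".
- **The only Week 24 reference.** It is stated in SAP 4.1.1 for efficacy alone: "For the changes from Week 24 at Week 48 in terms of DAS28-CRP, DAS28-ESR, HAQ-DI score, and FACIT Fatigue scale". No laboratory or vital-sign variable is named.
- **Laboratory tables.** SAP 4.6.2.2 plans "The summaries presenting a number of patients with new notable abnormalities (according to the protocol), as well as shift tables by toxicity grades", by treatment group and separately for each study period. It defines neither *new* nor the visit from which a shift starts.
- **Vital signs.** SAP 4.6.2.3: "new notable abnormalities (according to normal range criteria) will be presented by treatment group for each study period". No shift table is planned for them. Protocol 9.5.3 adds change from baseline by visit for both laboratory data and vital signs.
- **Notable laboratory values.** Protocol Table 12-1 applies to patients whose value is normal at baseline. Three of its 15 rows are relative to baseline: creatinine (rise above 50%), red cell count (fall above 20%) and hemoglobin ("> 20 g/L decrease from baseline").
- **SP2 safety objective.** Protocol 2.2 sets out to evaluate safety in continued and switched patients "as assessed by changes in vital signs, clinical laboratory parameters and incidence and severity of AE". It gives no reference visit.
- **Period boundary.** SAP 4.1.2 assigns assessments made on the SP2 start day to SP1, but does not name them as an SP2 baseline.

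**The concern.** The SP2 safety tables are meant to show what happens after patients move from Humira to GP2017, next to patients who stay on GP2017. Change after a switch is isolated by a value taken just before it. With Visit 2 as reference, the SP2 shift tables and baseline-relative flags also contain 24 weeks of change on the SP1 product, and that product differed between the two SP2 groups.

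Two laboratory errors follow. A change that arose in SP1 and persists can be shown in the SP2 table. A fall that begins after the switch can go unflagged because it started from a raised SP1 value. The SAP already uses Week 24 for SP2 efficacy change and dates adverse events to SP2 by their start, so the safety laboratory tables are out of line with the rest of the SP2 analysis. No reason is given.

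**Working it through.** The documents give no figure on this point, so there is none to reproduce. The check reads the rules together, then applies the hemoglobin limit with each reference.

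**1. Which baseline governs.** The rule is Visit 2 unless stated otherwise. The stated exceptions are DAS28-CRP, DAS28-ESR, HAQ-DI and FACIT. SAP 4.6.2.2 and 4.6.2.3 state none. Visit 2 therefore governs the SP2 laboratory tables. One consequence concerns who is eligible to be flagged: a patient abnormal at Visit 2 but normal at Week 24 is outside Table 12-1 in SP2, while one normal at Visit 2 but already abnormal at Week 24 is inside it.

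**2. Worked cases (invented values, g/L; flag if the value minus the reference is below -20).**

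| Visit 2 | Week 24 | Week 36 | Against Visit 2 | Against Week 24 |
|---|---|---|---|---|
| 130 | 108 | 108 | 108 - 130 = -22, flagged | 108 - 108 = 0, not flagged |
| 120 | 138 | 115 | 115 - 120 = -5, not flagged | 115 - 138 = -23, flagged |

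The first patient did not change after the switch. The second fell by 23 g/L after it.

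**3. Size, under assumptions.** Visit error SD is 5 g/L. Each patient has a lasting SP1 change with mean m and SD 8 g/L. There is no change in SP2. A patient is flagged if the lower of Weeks 36 and 48 is more than 20 g/L below the reference. None of these inputs is in the documents.

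A hand check for one SP2 visit with m = 0:
- Against Visit 2, the difference has SD sqrt(8² + 5² + 5²) = sqrt(114) = 10.7, so P = Φ(-20/10.7) ≈ 3.1%.
- Against Week 24, the lasting change cancels and the SD is sqrt(5² + 5²) = 7.07, so P = Φ(-20/7.07) ≈ 0.2%.

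Simulation with both SP2 visits:

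| Mean SP1 drift m (g/L) | No SP2 change: flagged, Visit 2 | No SP2 change: flagged, Week 24 | True 25 g/L fall: flagged, Visit 2 | True 25 g/L fall: flagged, Week 24 |
|---|---|---|---|---|
| +8 | 0.7% | 0.5% | 49% | 89% |
| +4 | 2.0% | 0.4% | 64% | 89% |
| 0 | 4.8% | 0.5% | 78% | 89% |
| -4 | 10% | 0.5% | 87% | 89% |
| -8 | 19% | 0.5% | 94% | 89% |

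The Week 24 columns do not depend on m. In the Visit 2 columns, upward drift hides real falls and downward drift over-flags.

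**4. If *new* means not flagged earlier in the study.** At m = 0, removing everyone already flagged in SP1 leaves 1.8% flagged against Visit 2 if the whole SP1 change is present from Week 4, and more if it builds up gradually. The Week 24 rate is 0.5%. This reading shrinks the carry-over but does not remove it, and it does nothing for missed falls.

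**5. Between-group effect.** Carry-over into the SP2 difference is (SP1 rate on Humira - SP1 rate on GP2017) × share persisting. With invented rates of 8% and 4% and half persisting, it is (8% - 4%) × 0.5 = 2 percentage points. With equal SP1 rates and equal persistence it is zero.

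**The case against.** A reader might infer that the SAP counts SP1 abnormalities as having arisen after the switch, and that falls are missed for laboratory data and vital signs alike. The documents do not say this. *New* is undefined and could be programmed as not seen earlier. Vital signs are judged by normal ranges, so a value that leaves the range after the switch is not hidden by a Visit 2 threshold. Twelve of the 15 Table 12-1 rows are absolute or ULN/LLN limits, so missed falls concern hemoglobin and red cell count, and only after an SP1 rise. All of this stands and limits the scope.

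Other outputs also soften the effect. Adverse events enter SP2 by start date (SAP 2.3.2.1 and 4.1.2). Laboratory data are listed in full and box plots are planned by treatment and period. Protocol 9.5.3 plans absolute laboratory values by visit, so Weeks 24, 36 and 48 can be compared directly. This stands in part. Protocol Appendix 1 makes a notable value an adverse event after three repeated measurements at later protocol visits, or sooner at the investigator's discretion. Safety samples in SP2 are scheduled only at Weeks 36 and 48, so for a change that begins in SP2 the three-measurement route cannot be completed within the period.

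Finally, Visit 2 suits the long-term safety objective, both groups share it, and no SP2 safety hypothesis is tested. That justifies Visit 2 for the entire-study tables, which SAP 2.7 and Section 3 add. It does not justify it for tables whose purpose is change after a switch.

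**Conclusion.** The point holds for laboratory data. In SP2, toxicity-grade shifts, the hemoglobin, red-cell and creatinine limits, the normal-at-baseline condition and change summaries run from Visit 2 by default, so they mix SP1 change with change after the switch. For vital signs, only the meaning of *new* and the protocol's change-from-baseline summaries are affected. Adverse events are unaffected.

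The direction of the error depends on SP1 drift, which is unknown: rising values hide later falls, and falling values produce excess flags. The percentages rest entirely on the assumed variability and drift and are illustrations, not forecasts. The documents do not support a claim that a false switch signal will appear between the groups, since that also needs SP1 effects that differ by product. This is a gap worth closing before unblinding. It does not touch the primary analysis.

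**What to change.** In SAP 4.1.1 add that, for SP2 summaries of laboratory data and vital signs, the reference is the last available assessment on or before the first SP2 dose, normally Week 24. The wording needs *last available* because Week 24 values are scheduled but not guaranteed. Use this reference in SP2 for change, toxicity-grade shifts, the baseline-relative Table 12-1 limits with their normal-at-baseline condition, and the meaning of *new* (not present at that reference). State the shift origin in SAP 4.6.2.2, and give the definition of *new* in both 4.6.2.2 and 4.6.2.3. Keep Visit 2 for the SP1 and entire-study tables, which serve the long-term objective.

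The cost is one extra baseline flag in the laboratory and vital-sign datasets and slightly more programming. No new data are needed.

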4.1.2 Study Period definitions

Day 1 of Study Period 1, i.e. the day on which the first dose of study medication is taken, is considered as the start for the SP1 and the study. All data before are considered belonging to Screening (SCR) period.

A patient is considered to have entered SP2 only if they have taken study medication assigned as belonging to SP2. The start of SP2 is defined as the first date of administration of study medication as assigned in SP2.

All data after study discontinuation (for AEs only in case they are after 30 days post last dose, see in Section 2.3.2.1) will be considered belonging to Follow-up (FUP) period. Concomitant medications started on day of discontinuation will be considered belonging to FUP period.

In cases where the last non-missing assessment and the start date coincide, the assessment will in general be considered pre-treatment (baseline), however AEs and medications commencing on the date of the first study medication injection will be considered post-baseline (SP1). Similarly, assessment on the day of the start date of SP2 will be assigned to SP1, while medications and AEs commencing on the day of the start date of SP2 will be assigned to SP2.

In the case of a partial date where it is unclear whether adverse events belong to SP1 or SP2 then they will be assigned to SP2. This is the more conservative assessment as all patients in SP2 are receiving the investigational product GP2017. Medications where it is unclear if they started in SP1 or SP2, i.e. there is a partial start date and no stop date in SP1, will be assigned to SP1 and reported in both periods.

Rules to impute partial dates for adverse events and concomitant medications for the purpose of assigning them to the correct study period are provided in [Appendix 1](#) and [Appendix 2](#). Completely missing dates will not be imputed.

4.1.3 Study day

Study day will be calculated from the reference start date, and will be used to show start/stop day of assessments and events.

Reference start date is defined as the day of the first dose of study drug administration (Day 1) and will appear in every listing where an assessment date or event date appears.

If the date of the event is on or after the reference date then:

Study Day = (date of event - reference date) + 1

If the date of the event is prior to the reference date then:

Study Day = (date of event – reference date)

In the situation where the event date is partial or missing, Study Day, and any corresponding durations will appear missing in the listings.

4.1.4 Visit windows

Study data for a scheduled visit (weeks 2, 4, 12, 24 and 48) should be entered on to the correctly designated eCRF page for that visit. However, in order to be considered per protocol a visit needs to fall within a window of time around the target date for the visit. In the protocol this is defined as a window of ± 2 days for SP1 and ± 3 days for SP2 around the target date, calculated from baseline (first dose date of IMP). Assessments that fall outside of this window will not be considered as being per protocol. However, all such assessments will be included into analysis and listings.

For the patients who early discontinued from the study, the End of Study visit will be mapped to the corresponding scheduled visit based on the study day.

4.1.5 Duration

All duration variables in days will be calculated as end date – start date + 1.

To get duration in month duration in days will be divided by 30.4375; duration in years – by 365.25.

4.2 Disposition of patients and protocol deviations

Frequency and percentage of patient's recruitment by region, country, site, and treatment group will be presented.

Disposition of patients includes the number and percentage of patients for the following categories: randomized, completed Week 12, discontinued before Week 12, completed SP1, discontinued during SP1, eligible to enter SP2 (achieving at least a moderate EULAR response assessed by DAS28-CSR at Week 24), entered SP2, completed SP2, discontinued during SP2. The primary reason for discontinuation in SP1/SP2 will be summarized.

A patient who completed the Visit 14 (Week 24) is considered to have completed SP1.

Frequency and percentage of patients having major and minor protocol deviations will be presented by deviation category, treatment group and overall for all patients in FAS. Patient having major and minor protocol deviations will be counted only once under more severe deviation category. Patients who are excluded from each analysis population and protocol deviations will also be listed.

All percentages for the summaries will be based on the number of patients in FASs (SP1 FAS for study period 1 and during the entire study, or, SP2 FAS for study period 2).

4.3 Demographics and baseline characteristics

4.3.1 Demographic and baseline disease characteristics

Demographic characteristics include categorical data (i.e., sex, race, and ethnicity) and continuous data (i.e., age, height, body weight, and body mass index [BMI]) will be summarized.

Age (years) = INT ((date of ICF – date of birth)/365.25)

The randomization stratification factors including region, weight category as per CRF and IRT, and prior therapy as per CRF and IRT will be summarized.

RA disease history will include duration since initial diagnosis of rheumatoid arthritis (in years), current global functional status in RA according to ACR, number of previous DMARDs used, previous MTX duration (in months), baseline MTX dose, and number of not assessable joints on baseline (out of 28 and full joint counts).

When counting the number of not assessable joints (out of 28/68) at baseline, in case a joint is not assessed at baseline, but assessed on screening or post-baseline visits (i.e. there was no underlying medical reason such as surgery), the joint will be considered assessable.

Partial dates of initial diagnosis will be imputed by earliest possible date (i.e. first day of month and 1st of January). MTX and DMARD treatments will be assessed using ATC coding. When

counting the number of DMARDs (excluding MTX) only distinct medications should be counted.

Previous MTX duration will be calculated from the date of earliest recorded MTX intake (partial dates will be imputed according to [Appendix 2](#)) up to date of first dose of study treatment.

RA baseline disease characteristics will include baseline values of: DAS28-ESR, DAS28-CRP, number of tender/swollen joints (TJC68, SJC66, TJC28, SJC28), CRP (mg/dL), ESR (mm/h), rheumatoid factor (positive/negative), anti-CCP antibodies (positive/negative), and the three VAS assessments (physician, patient, pain).

Other baseline characteristics (e.g. FACIT scores, HAQ-DI scores, tuberculosis, hepatitis and pregnancy screening) will also be presented in a summary table.

Summaries for continuous and categorical variables (as described in Section [2.1.2](#)) will be presented for each treatment group and in total. All data will be listed.

4.3.1.1 Incorrect Stratum assignment

A table will be produced for each stratification factor which shows the number of patients in each of the strata assigned by the IRT system compared to the number of patients who should have been included into each stratum according to the clinical database. All stratification factors will be listed.

4.3.2 Medical history

Relevant medical history/current medical conditions not related to rheumatoid arthritis will be summarized and listed by Medical Dictionary for Regulatory Activities (MedDRA) coding dictionary (version 20.0) system organ classes (SOC) and preferred terms (PT) on SAF. Medical history shall be presented separately for those conditions active/not active at start of study.

Number of patients with medical history and current conditions will be summarized separately using frequency and percentage of patients. Medical conditions with a stop date on or after the dose of first medication are classified as current medical conditions. Medical conditions marked as “Ongoing” are also considered as current medical conditions for presentation. Medical conditions without ongoing ticked or a stop date before the dosing of first study medication are considered to have resolved, and are classified as previous medical history. Medical history details will also be listed. If the stop date is present and before the dosing of first study medication then the event is considered as medical history. In the case of a partially present stop date, if the day is missing then impute the last day of the month unless month is same as month of first dose of study drug then impute last dose date; if the month and day are missing then impute 31st December unless year is the same as first dose date then impute last dose date. Imputed partial stop dates will only be used to assign conditions to medical history or current conditions, and the partially complete date will be used in listings.

The summaries will be presented by primary system organ class (SOC) and preferred term (PT) for each treatment group and in total. A patient will be counted only once within the SOC and PT if the patient has multiple medical conditions within the same SOC and PT.

